The study proposes to conduct a stepped-wedge, cluster-randomized implementation trial of a novel, user-centered implementation strategy for the delivery of TB contact investigation at 12 TB diagnostic and treatment units (DTUs) located at health facilities in central Uganda. The trial over will proceed over the course of 16 trial steps, each 8 weeks in duration, with the intervention period lasting from as little as 16 weeks up to 56 weeks at the participating facilities. We will use a complete stepped-wedge design, including an 8-week transition period for training and initial adoption, followed by 8 to 52 weeks of post-intervention data collection at each site. Data collected during the transition periods will not be included in the final analysis. In addition, the trial will be paused for 6 weeks during the annual 2022-2023 year-end holiday period (12 December 2022 through 15 January 2023; all transition periods falling during and after this pause period will be delayed by six weeks and patients recruited during this period, as well as the data of their contacts, will be excluded from the trial.[§] The rationale for this pause is that staffing levels and patient visits are low during this period, and without exclusion, this could bias the trial results in uncertain ways.

§Version 2.0 Update: On 15 October 2022, the President of Uganda announced Ebola-related public health restrictions preventing public movement in two districts where two study sites are located: Mubende and Kasambya. As a result, the principal investigators immediately paused all new introductions of the study intervention effective immediately for the subsequent 8-week period ending 11 December 2022, effectively extending the previously proposed 6-week study pause by at least 14 weeks. The original schema is shown below in Figure 1, and an updated schema is shown below in Figure 2.

[figure not shown]

Figure 1. HCD-CoP Intervention Randomization and Enrolment Schedule.

Legend: Ordinal numbers indicate the cross-over sequence from standard to the intervention period. Note that pause periods are not shown in the current figure.

Group	Site	Month																	
		1 Mar 7 - Apr 3	2 Apr 4 - May 1	3 May 2 - May 29	4 May 30 - Jun 26	5 Jun 27 - Jul 24	6 Jul 25 - Aug 21	7 Aug 22 - Sep 18	8 Sep 19 - Oct 16	9 Oct 17 - Nov 13	10 Nov 14 - Dec 11	Holiday	11 Dec 12 - Jan 15	12 Jan 16 - Feb 12	13 Feb 13 - Mar 12	14 Mar 13 - Apr 9	15 Apr 10 - May 7	16 May 8 - Jun 4	17 Jun 5 - Jul 2

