- a) *Outcome definition:* Number of contacts who complete TB evaluation within 60 days (ctevalcomplete60) of index patient treatment initiation divided by the total number of contacts screening TB symptom positive (ctevaleligible). This will be an aggregate, cluster-level, exposure-specific (control versus intervention) measurement.
- b) *Outcome analysis:* Difference in log odds of the outcome between the intervention and control exposure periods using the Logit model (*n.b.*, this will be the same for all proportional outcomes)

Secondary Outcomes

- a. **Effectiveness** (*i.e.*, clinical effectiveness)
 - i. Proportion of contacts diagnosed with active TB (also known as the active TB treatment yield of TB contact investigation, or the number needed to screen):
 - a) *Outcome definition:* Number of contacts diagnosed with active TB (definitions below) and initiated on treatment within 60 days of index patient treatment initiation divided by the total number of contacts encountered.
 - (i) Microbiologically confirmed active TB: Diagnosed by a positive AFB-smear microscopy result, GeneXpert result, or other accepted *Mtb*-specific microbiologic test (*e.g.*, urinary LAM or mycobacterial culture)
 - (ii) Clinically confirmed active TB: Active TB diagnosed clinically, based on clinically diagnosed extra-pulmonary TB or a decision to initiate presumptively for active pulmonary TB.
 - b) *Outcome analysis:* As above
 - ii. Proportion of contacts initiating TB preventative therapy (TB preventative therapy yield of TB contact investigation):
 - a) *Outcome definition:* Number of TB contacts initiated on TB preventive therapy within 60 days of index patient treatment initiation divided by the total number of contacts eligible for TB preventive therapy
 - (i) Children under age 5
 - (ii) Persons living with HIV
 - (iii) Older adolescent (age ≥ 15 years and adult household and other close contacts with a positive TST and in whom active TB has been excluded by symptoms and/or testing)
 - b) *Outcome analysis:* As above
- b. **Public Health Impact** (*i.e.*, public health effectiveness)
 - i. Count of contacts diagnosed with active TB:
 - a) *Outcome definition:* Number of contacts diagnosed with active TB (definitions below) and initiated on treatment within 60 days of index patient treatment initiation
 - (i) Microbiologically confirmed, as defined above
 - (ii) Clinically confirmed, as defined above

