Merged datasets will be extracted from CommCare, transferred to Stata, and re-arranged into working analytic files and checked for completeness. We will generate time-slice and exposure variables including the control-intervention exposure defining variable (var), the cluster-month var, cluster-exposure var, exposure-month var, and the exposure-time-cluster variable. The transition period will be excluded from the analysis as indicated in the trial design section 2.1 above.

There are 12 study sites that were assigned into six groups (2 facilities per group) and one group at a time will be switched from the standard pre-intervention to the user-centered implementation strategy during 8-week training and transition intervals in a randomly assigned order. Within each of the 6 groups, cluster-level covariates (outcomes, predictors, and confounders) will be formed by aggregating individual-level participants' data. For every cluster, each outcome (primary, secondary, and implementation) occurring

during the study period will be assigned to that cluster, the exposure condition (pre-intervention or intervention), and the trial month in which it occurred. A group-specific summary measure of the outcome, Y_{ij} (for i exposure and j period) will be calculated as a mean (SD) for continuous and count variables, and mean proportion for binary variables. From the Y_{ij} s, we will then calculate the cluster-period summaries $\Sigma Y_{ij} / n$, where n =number of months in i exposure, and estimate unadjusted period-specific intervention effect (θ) based on these cluster-period summaries.

b. Baseline assessment and trend analysis

Baseline measures of all outcomes will be calculated using data collected in the pre-intervention period months 1 and 2 (Figure 1).

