Within-period analyses comprise period-specific assessments where aggregated outcomes of groups in the pre-intervention exposure are compared with those of groups receiving the intervention exposure during the same trial month(s). For between-period analyses, outcomes for each group are compared to those of the same group in the intervention versus pre-intervention exposures, *i.e.*, cluster-specific, control-intervention comparisons across different time periods. Post-baseline measures will include pre-intervention and intervention exposure since groups will enter intervention exposure at varying times. For clusters still in the control exposure period, each subsequent trial month after study month 2 before the commencement of their transition period will be analyzed as the pre-intervention, post-baseline period. The start of effective intervention exposure (*i.e.*, the post-transition period) for each group will be the first day of the calendar month following the 2nd month of the transition interval.

c. Intervention Effect Analysis

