3.1.2 Populations and subgroups to be analyzed

a. Populations

- **Intention-to-treat (ITT):** The primary analysis will consider the intention-to-treat population, including all index patients eligible at all sites and their identified and screened contacts. Pre-intervention patients in the intention-to-treat population will be those who were diagnosed at a site during the pre-intervention period, and subsequently, their contacts will be considered pre-intervention contacts. Intervention period patients in the ITT population will be those who were diagnosed with TB at a site during the intervention period, and subsequently, their contacts will be considered intervention contacts.
- A per-protocol analysis is not relevant in this case since all community health workers at the site during the intervention period will be exposed to the user-centered implementation strategy, and it is not possible to quantitatively measure adherence to the implementation components in the context of the pragmatic features of the trial.

b. **Adjusted analyses:** In the presence of secular trends (and thus analysis at the individual level), the adjusted analyses will consider age (continuous), sex, HIV status, and any other baseline characteristics found to be imbalanced between control and intervention periods. In the absence of secular trends (and thus aggregated analysis by site and by month), the adjusted analyses will consider covariates such as the proportion of male vs. female, mean age, health center level, health center location (peri-urban vs. rural), and GDP of health center district (low vs. high). Data will be collapsed by the sum of total outcomes for binary outcome variables and mean value for any continuous variables (e.g., age). We will adjust for trial period as appropriate for stepped wedge trial data analysis.

c. **Subgroup analyses:** In the case of individual patient data analysis, five subgroups will be analyzed using the ITT population.

- Age
- Sex: All eligible patients at randomized health centers will be divided into two groups by sex and analyzed separately.

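### The SAP sets exposure by the index patient's diagnosis date but does not carry that date through to trial month or transition exclusion, so its literal rules can bias the primary estimate in either direction

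*SAP*

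**What the plan says.** Four places in the SAP bear on where a contact's data go.

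- **3.1.2 Populations, intention-to-treat.** "Pre-intervention patients in the intention-to-treat population will be those who were diagnosed at a site during the pre-intervention period". Each contact takes the exposure of the index patient who named them. Intervention patients and contacts are defined in the same way. An index patient diagnosed in the transition is given neither exposure.
- **Statistical Methods, a. Dataset assembly.** Every outcome, with the primary named among them, "will be assigned to that cluster, the exposure condition (pre-intervention or intervention), and the trial month in which it occurred". On the transition it says only: "The transition period will be excluded from the analysis as indicated in the trial design section 2.1 above".
- **Trial Design.** For the transition: "Data collected during the transition periods will not be included in the final analysis". For the holiday pause: "patients recruited during this period, as well as the data of their contacts, will be excluded from the trial".
- **Primary Outcome.** The numerator is contacts completing evaluation within 60 days of index treatment initiation. The denominator is all contacts who screened symptom positive, including those who never complete.

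The month matters because section b, Baseline assessment and trend analysis, compares groups within the same trial month, and Equations 1 to 4 carry period terms. The start of effective exposure is also worded in two ways: the first Monday after the 8-week transition (opening of Statistical Methods) and the first day of the next calendar month (section b).

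**The concern.** The 60-day window is longer than the 56-day transition, and contact-investigation attempts continue to the two-month refill visit (Evidence-based Practice section). A contact of a control index patient can therefore complete evaluation after the site has entered transition. The SAP leaves three things open:

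1. Which trial month that contact belongs to.
2. Which month holds a symptomatic contact who never completes, and so has no month of occurrence.
3. Whether the transition exclusion removes index patients diagnosed in the transition, or only events dated in it.

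Two analysts who both follow the SAP could build different primary datasets. The resulting errors do not share a direction, so the choice cannot be defended as conservative.

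**Working it through.** **Inputs from the documents.** Transition 56 days, outcome window 60 days, six groups of two sites crossing every 8 weeks from month 3. On the original schedule group g has 56g control days, in total 56 × (1+2+3+4+5+6) = 1,176. Planning values: 11 index patients per clinic per 8-week block, 1 symptomatic contact each, completion 0.40 against 0.60.

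**Inputs assumed.** The documents give no delay from index date to completion. I used an exponential delay with median 7, 14 or 21 days, cut at 60, and a uniform delay over 0 to 60 days as an extreme. The 7 days echoes the SAP's target for the community visit. I also assumed 16 four-week months, constant inflow, treatment starting at diagnosis, and no carry-in from the run-in.

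**The plan's own figure.** N = m × g × T × K = 1 × 11 × 7 × 12 = 924, as stated. It does not depend on the placement rule and is not in dispute.

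**Overlap.** Control index-days with the window still open at transition start: 56 (all of Group 1) + 5 × 60 = 356, and 356/1,176 = 30%. Planned control contacts number 42 clinic-blocks × 11 = 462, so about 140 are affected.

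**Control completions falling at or after transition start.** Share = Σ E[min(L, 56g)] / 1,176, where L is the delay.
- Exponential, median 7 (mean about 9.9 days after the cut): 6 × 9.9/1,176 = 5.1%. Group 1: 9.9/56 = 17.7%.
- Uniform: Group 1 is 56 − 56²/120 = 29.87 days, or 53.3% of 56. Overall (29.87 + 5 × 30)/1,176 = 15.3%.
- Of 462 × 0.40 = 185 control completions, that is 9 to 28.

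**Effect on the estimate.** I computed expected completions by group and month, dropped transition months, and fitted a Poisson log-link model: log E(Y) = log n + group + month + θX. The table gives exp(θ). The null has completion 0.40 throughout. Where four values are given, they follow the order of the delays above.

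| Placement | Null | True 1.50 |
|---|---|---|
| (i) Exposure and month by index date (3.1.2); transition-diagnosed patients dropped; completions dated in the transition not counted (Trial Design) | 1.17, 1.32, 1.40, 1.66 | 1.72 to 2.36 |
| (i) with those contacts removed entirely | 1.10 to 1.39 | not tabulated |
| (ii) Completions dated by occurrence; denominators at index date; transition-diagnosed patients dropped | 0.85, 0.75, 0.70, 0.58 | 1.25, 1.09, 1.01, 0.82 |
| (iii) Dated by occurrence; later outcomes of transition-diagnosed patients kept; transition-phase rate 0.50 | 1.00 | 1.46, 1.43, 1.41, 1.37 |
| (iv) One index-patient date for everything | 1.00 | 1.50 |

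In (i) only control index patients have a transition ahead of them, so only control completions are lost. The crude ratio would be 1/(1 − 0.051) = 1.05 to 1/(1 − 0.153) = 1.18. Period adjustment enlarges it, because the losses sit in the control months next to each crossover, which weigh heavily in such a fit. In (ii) the first intervention months have full denominators but few completions. In (iii) those months take in completions generated at the lower transition rate. With a transition rate of 0.40 a true 1.50 reads 1.24 to 1.42, and with 0.60 there is no dilution. Rebuilding the model on a different time grid moves these values by no more than about 0.01.

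**The case against.** **Exposure is settled.** A reader might infer that the SAP has no rule for exposure. It has one: 3.1.2 is explicit, belongs to the primary analysis, and is more specific than the dataset-assembly sentence, which can be read as dating the month only. That stands. It does not supply a month for non-completers, nor say whether a control contact's completion during the transition counts.

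**The two exclusions do not contradict each other.** One covers the transition and the other the holiday pause. They are different windows with different anchors. The pause wording shows only that a patient-based exclusion was written once and not for the transition.

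**Reading (ii) splits one record.** The SAP aggregates individual data, and Equation 1 puts each individual in one period, which argues for keeping a contact's numerator and denominator together. That also stands: 0.58 to 0.85 arises only if they are dated separately, and should not be taken as the bias to expect. If every contact, non-completers included, moved by one date and transition-diagnosed patients were dropped, the null would be 1.00. The contact interview date is a candidate, but the SAP does not name it for this purpose.

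**Period terms as protection.** A reader might infer that a false benefit cannot arise once period terms are in the model. Reading (i) has them and still gives 1.17 to 1.66 under the null.

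**The inputs.** All delays are assumed, the uniform one is extreme, and the schedule is the original rather than Figure 2 with its Ebola and holiday pauses. This limits the sizes but not the gap in the text.

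**Conclusion.** The point holds as a gap between stated rules. Exposure follows the index diagnosis date, but month and transition exclusion are worded by when an outcome occurred or data were collected. Combining those sentences literally can give a false benefit (i), an apparent harm (ii) or dilution of a true effect (iii), all with period adjustment. Reading (i) deserves most attention, because it needs only 3.1.2 for exposure and month plus the Trial Design sentence on transition data. Even at a median delay of 7 days it moves the null to 1.17. The sizes rest on the assumed delays, constant inflow and the original schedule. They show direction and possible scale and are not estimates for this trial. The documents do not show that any one of these readings will be used. The SAP should be changed before the primary dataset is built.

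**What to change.** Replace the occurrence-month sentence under dataset assembly and the data-collected wording in Trial Design with one rule: *the index-patient date that defines exposure in 3.1.2 also sets trial month or period, numerator, denominator and transition exclusion for all of that patient's contacts.* Then:

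- Exclude index patients dated in the transition, with their contacts, as is already done for the pause.
- Count completions through day 60 for every included contact, even when they fall in the transition. The 60-day clock may still start at treatment initiation.
- Add a sensitivity analysis omitting control index patients dated within 60 days before their site's transition.
- Align the first-Monday and calendar-month wordings for the start of effective exposure.

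The cost is SAP wording and one derived variable. The rule has a downside: some control follow-up overlaps the transition, and if the new strategy already helps those contacts, a true effect is diluted. If control completions in the transition run at an assumed 1.25 times the control rate, a true 1.50 reads 1.36 to 1.45. The 60-day omission recovers 1.50 in that model, but on the original schedule it removes 30% of control index-days, including all of Group 1's. It should therefore remain a sensitivity analysis, and the share removed should be recomputed on the Figure 2 schedule.
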